Prevalence of Gastroesophageal Reflux Disease, Its Association With Eating Behavior and Psychological Disturbance, and Its Impact On Quality Of Life, Among Medical Students In The MENA Region, A Multinational Cross-Sectional Study

NCT registration: Not yet registered

Document data: 5 August 2025

Introduction

Gastroesophageal reflux disease (GERD) is a common gastrointestinal disease. It is a chronic condition that is characterized by the regurgitation of stomach contents into the esophagus and is associated with heartburn. The occurrence of these symptoms for at least two weeks increases the likelihood of having GERD. Other GERD symptoms include chest pain, nausea, dysphagia, burping, water brash, and vomiting(Argyrou et al., 2018; Richter & Rubenstein, 2018). All these symptoms negatively affect the patients' quality of life. The pathophysiology of GERD is multifactorial(Lee & McColl, 2013). Several factors have been suggested to cause GERD, including a hypotensive lower esophageal sphincter (LOS) and a defect in the gastric sling/clasp muscle fiber component(Hershcovici et al., 2011; Orlando, 2001).

The global prevalence of GERD is about 13.98%(Nirwan et al., 2020) with variation among different countries and ethnic groups. In East Asia, it ranges from 2.5% to 7.5%, 8.5 to 25.9% in Europe, 18.1% to 27.8% in South and North America, and about 11.6% in Australia. In the Middle East, it ranges from 8.7% to 33.1%(El-Serag et al., 2014).

Several risk factors have been identified that increase the likelihood of having GERD. Obesity was found to be one of the risk factors that increases GERD. Also, dietary habits such as spicy food, coffee drinks, or administering NSAIDs increase the prevalence of having GERD(Jarosz & Taraszewska, 2014).

On the other hand, psychological factors also play an important role in GERD severity. Both stress and anxiety are linked to an increase in GERD. A previous study showed that stress can increase heartburn symptoms in patients with heartburn(He et al., 2022) and also increase in anxiety level was associated with an increase in esophageal reflux(Song et al., 2013). Finally, depression was found to be associated with GERD, which can be explained by a change in the eating behavior in depressed patients(Mohammad et al., 2019).

Rationale

Medical students suffer from a study burden, which increases their level of anxiety and stress. They also have a higher likelihood of having trouble with eating behavior or having a lot

of coffee daily. This increases their likelihood of having GERD. In the Middle East, fewer studies have assessed the effect of GERD. A recent cross-sectional study assessed the prevalence of GERD among medical students in Egypt. They found a prevalence of 17.1%. They found an association between increasing stress levels and increasing GERD severity. Also, smoking was a significant risk factor for GERD symptoms. Another cross-sectional study among medical students in 21 universities in Egypt. They reported a prevalence of 28.4%. Again, they found that an increasing level of stress and anxiety was associated with increasing GERD severity. Finally, Two cross-sectional studies were conducted in Saudi Arabia. They reported a prevalence of 23.8% and 23.1% respectively. To our knowledge, no study has assessed the GERD and its related quality of life among medical students in Middle East and linked their findings with eating behaviour

Research Questions

1. What is the prevalence of GERD among medical students and interns, its risk factors, its impact on health-related quality of life, and psychological disturbance?
2. What is the impact of eating behavior on GERD prevalence?

Aim

To improve the quality of life among medical students and interns in the Middle East countries

Objectives

1. To assess the prevalence of GERD among medical students and interns in the Middle East
2. To assess the effect of GERD on health-related quality of life
3. To assess the associated risk factors of GERD
4. To assess the impact of eating behavior on GERD prevalence
5. To assess the impact of stress, anxiety, and depression on increasing GERD prevalence

Methodology

Technical design

1. **Study design:** Cross-sectional study

2. **Setting:** Medical students in some Middle East countries (Egypt, Sudan, Somalia, Libya, Morocco, United Arab Emirates, Jordan, Saudi Arabia, Yemen, Iraq, and Palestine)
3. **Time:** From August 2025 to December 2025
4. **Population:** Arabic Medical students and interns in the MEAN region

5. Inclusion Criteria

- Medical students and interns studying medicine in the Middle East countries
- Have access to online platforms

6. Exclusion Criteria

- Students or interns who refused to participate

7. Sampling

We calculated the total sample size using Epi Info version 7.2.60(Epi InfoTM | CDC, n.d.) Assuming a 28.4% (Essa et al., 2024) prevalence rate and a 5% error margin with a 95% confidence interval, the sample size required for each country is 312. After adding a 10% nonresponse rate, the final sample size is about 343 for each country, so the total sample size will be 3773

8. Sampling Technique: Convenience Sampling

Operational design

1. **Pilot:** We will perform a pilot study in each country before starting the study to assess the readiness of the questions and the reliability of the questions via the Cronbach's alpha test.
2. **Study field:** an online questionnaire will be shared via an online platform with the target population.

3. Data collection method

An online questionnaire will be shared via social media platforms, including Facebook, WhatsApp, and Telegram.

The questionnaire consists of 6 sections

- The first section discusses the importance of the study for the participants, informing them that their data will be used only for research purposes, and obtaining informed consent
- The second section asks about the sociodemographic data and associated risk factors such as age, sex, residency, GPA, smoking, BMI, and eating habits
- The third section contains the GERDQ questionnaire(Jones et al., 2009). It is composed of 6 Likert scale questions that ask about GERD symptoms such as heartburn, nausea, and regurgitation. Each question has 4 answers scored from 0 to 3, making a rank from 0 to 18. If the participant scores 8 or more, this diagnoses GERD. Furthermore, the symptoms severity can be assessed. A score of 0-2 makes 0 % of having GERD, 3-7 makes a 50% likelihood of having GERD, 8-10 makes a 79% and 11-18 makes a 89% of having GERD. This questionnaire has a sensitivity being 65% and a specificity being 71% to diagnose GERD
- The Fourth section asks about the quality of life for GERD patients. We used the GERD-HRQL(Velanovich, 2007). This is a 16 Likert scale questionnaire that asks about the effect of GERD symptoms on the quality of life. The first 15 questions had 6 answers, ranging from no symptoms to Symptoms that are incapacitating – unable to do daily activities. This score ranges from 0 to 75. The sixteenth question asks about the present condition. The quality of life is calculated via the first 15 questions (scores from 0 to 75), with higher scores indicating lower quality of life.
- The fifth section asks about eating behavior. We used the Dutch Eating Behavior Questionnaire (DEBQ)(van Strien et al., 1986). This is a 33 Likert scale questionnaire that assesses the eating behavior in three items (retained eating, emotional eating, and External eating). Each question is composed of 5 answers (from never to very often) and scores range from 1 to 5.

- The final section asks about stress, anxiety, and depression using the DASS-21(Lovibond & Lovibond, 2015) questionnaire. This is composed of 21 Likert scale questions, each had 4 answers scored from 0 to 3. The scale is divided into 3 sections to assess depression, stress, and anxiety. The cumulative score for each part will be multiplied by two for interpretation of the severity of each section.
 1. For the Depression score, 0-9 indicates a normal person, 10-13 indicates mild symptoms, 14-20 indicates moderate, 21-27 indicates severe symptoms, and 28+ indicates extremely severe symptoms.
 2. For anxiety scores, 0-7 indicates a normal person, and (8-9), (10-14), (15-19), and 20+ indicate mild, moderate, severe, and extremely severe levels of anxiety.
 3. For stress scores, 0-14 indicates a normal person. A score of (15-18), (19-25), 26-33), and 34+ indicate a mild, moderate, severe, and extremely severe levels of stress.

4. Statistical analysis

First, data will be summarized according to its type. Categorical data will be summarized using frequency and percentage. Continuous data will be tested for normality. If the data is normally distributed, we will summarize it using mean and SD, and if not, median and IQR will be used. We will assess the difference between the population according to their sociodemographic data using a Chi-square and a Mann-Whitney U test. A p-value of <0.05 will be used as a cutoff point for statistically significant results. We will assess the correlation between all continuous data (GERD, GERD-HRQL, DEBQ, and DASS-21). Finally, a multiple linear regression test will be used to assess the relationship between the assessed variables.

Administrative design

1. Ethical consideration

- The study protocol will be approved by the Institutional Review Board of Zagazig University, Faculty of Medicine
- Study participants will be included after informed consent.

2. Confidentiality and data retention

Data collected will be kept confidential.

3. Risks and benefits of the participants

There is no cost for this study

Results

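### Research question 2 and Objectives 2, 4 and 5 ask for effects, but one cross-sectional questionnaire analysed by correlation and an unspecified linear regression can show association only

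*Combined protocol and SAP*

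**What the plan says.** The Technical design describes a cross-sectional study. Under Operational design, item 3, the GerdQ, GERD-HRQL, DEBQ and DASS-21 are sections of one online questionnaire. No follow-up and no time ordering of the measurements is described.

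The aims are worded as follows:

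- Objective 5: "To assess the impact of stress, anxiety, and depression on increasing GERD prevalence".
- Objective 2: "To assess the effect of GERD on health-related quality of life".
- Objective 4 and research question 2 both ask about the impact of eating behavior on GERD prevalence.
- Research question 1 asks about the prevalence of GERD, "its risk factors, its impact on health-related quality of life, and psychological disturbance".
- The title uses different words for different relations: "Its Association With Eating Behavior and Psychological Disturbance, and Its Impact On Quality Of Life".

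Under Operational design, item 4 (Statistical analysis), the four scores are to be correlated with one another, and then "a multiple linear regression test will be used to assess the relationship between the assessed variables". No dependent variable, list of explanatory variables or covariate set is given. Nothing in the plan limits interpretation to association. GERD is defined in item 3 as a GerdQ score of 8 or more.

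**The concern.** The objectives ask for directional effects, and the design and analysis have no direction in them. Followed as written, the plan would answer Objective 5 with an association and describe it in causal words. That answer would look the same if reflux symptoms simply lowered mood, or if a third factor such as workload drove both.

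Two further gaps make this worse. First, Objectives 4 and 5 are about prevalence, a yes/no status, while the only multivariable model is linear and has no stated outcome. No stated model clearly estimates what those objectives ask for, and the choice of outcome is left open until after the data are seen. Second, research question 1 does not make clear whether psychological disturbance is something GERD acts on or a separate item in the list.

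**Working it through.** **1. Inputs from the plan.** The prevalence of 28.4% and the total sample of 3773 come from Technical design, item 7 (Sampling). They reproduce: 1.96² × 0.284 × 0.716 / 0.05² = 312.5 (stated 312); 312 × 1.10 = 343.2 (stated 343); 343 × 11 countries = 3773. The point does not turn on these figures; they only set the scale below.

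**2. Can the planned analysis tell the directions apart?** A correlation is the same in either direction. For linear regression with a fixed set of covariates, the test of the adjusted association depends only on the partial correlation r: t = r × √[df / (1 − r²)]. Since r² is the product of the two adjusted slopes, t is the same whichever variable is called the outcome.

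This was checked on simulated data with N = 3773, two covariates and therefore df = 3769. The effect sizes are assumptions.

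| Simulated truth | Slope, GERD on distress | Slope, distress on GERD | t in both fits |
|---|---|---|---|
| Distress acts on GERD (0.3) | 0.290 | 0.271 | 17.93 |
| GERD acts on distress (0.3) | 0.271 | 0.290 | 17.93 |
| Unmeasured common cause, no direct effect | 0.337 | 0.349 | 22.40 |

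For the first row, r² = 0.2897 × 0.2712 = 0.0786, so r = 0.280 and t = 0.280 × √(3769 / 0.9214) ≈ 17.9. The first two rows are mirror images because they use the same random draws. What matters is that the two fits agree within each row. Naming an outcome would complete the specification but would not identify a direction.

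**3. Illustration on the prevalence scale.** Suppose stress has no effect on GERD, and GERD raises a normally distributed stress score by d SD. Both the normal shape and d are assumptions; the prevalence p = 0.284 is the plan's. Let c be the cut-off for the overall top quartile, which solves p × [1 − Φ(c − d)] + (1 − p) × [1 − Φ(c)] = 0.25. Let a = 1 − Φ(c − d) and b = 1 − Φ(c) be the shares above c with and without GERD. Then:

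- GERD in the top quartile = p × a / 0.25
- GERD in the rest = p × (1 − a) / 0.75
- odds ratio = [a / (1 − a)] / [b / (1 − b)]

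| d | c | a | b | GERD, top quartile | GERD, rest | Odds ratio |
|---|---|---|---|---|---|---|
| 0.2 | 0.734 | 0.2967 | 0.2315 | 33.7% | 26.6% | 1.40 |
| 0.3 | 0.766 | 0.3207 | 0.2219 | 36.4% | 25.7% | 1.66 |
| 0.5 | 0.833 | 0.3697 | 0.2025 | 42.0% | 23.9% | 2.31 |

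**4. Reading research question 1 against the rest.** The phrase "its impact on health-related quality of life, and psychological disturbance" can be read as GERD acting on psychological disturbance, the reverse of Objective 5. The comma also lets psychological disturbance stand as its own item. The title uses association for it and keeps impact for quality of life. Objective 2 limits the effect of GERD to quality of life, and no objective runs from GERD to psychological disturbance. These places favor the reading without a direction.

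**The case against.** The best defense is that the causal words are loose usage. The plan calls itself cross-sectional, Objective 3 speaks of associated risk factors, and the analysis section promises only correlations and a relationship. It contains no causal estimator, no interpretation rule and no success criterion for Objective 5, so how the result would be reported is a prediction. Part of this stands: nothing shows that the authors intend a causal analysis. But the title itself separates association from impact, so the words are not interchangeable within the document, and Objective 5 goes further than the title does.

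It is also fair to say that the odds ratios measure no flaw specific to this plan. The shifts are assumed, no top-quartile comparison is planned, and the same figures would arise after the rewording. They show only that an association has no direction.

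A reader might infer that research question 1 contradicts Objective 5, so that one association would be claimed as support for both directions. The documents do not establish this. The sentence in research question 1 is ambiguous, and the title and Objective 2 favor the reading under which there is no conflict.

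**Conclusion.** The point holds as a mismatch between the wording of the aims and what the design and analysis can deliver. Research question 2 and Objectives 2, 4 and 5 are directional; the data and the planned methods support association only. The outcome of the regression is unnamed, and no stated model clearly targets the binary prevalence in Objectives 4 and 5. Research question 1 needs clarifying.

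The range of 1.40 to 2.31 is an illustration that rests on normal scores, an assumed rise of 0.2 to 0.5 SD and the plan's 28.4% prevalence. It should not be read as the expected bias in this study. No corrected figure for the plan follows from it, and the sample size is unaffected. The change is worth making before analysis because it alters both what is modelled and what may be concluded, at little cost.

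**What to change.** 1. In research question 2 and Objectives 2, 4 and 5, replace the words for effect, impact and increase with association.
2. Reword research question 1 so that psychological disturbance is a factor associated with GERD, in line with the title. This clarifies the sentence; it does not remove a direction that the plan is known to contain.
3. For Objectives 4 and 5, replace the unspecified multiple linear regression with a binary-outcome model, for example logistic regression. The dependent variable is GerdQ 8 or more, and the DEBQ subscale and DASS-21 scores are explanatory. Covariates come from what the study collects, such as age, sex, smoking and BMI, together with country.
4. For Objective 2, keep linear regression, with the GERD-HRQL score named as the dependent variable and GERD as the explanatory variable.
5. State in the Statistical analysis section that conclusions are limited to association.

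The cost is some rewording of the questions and objectives and a short model specification. No new data or participants are needed. The downside is a more modest headline conclusion.

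### Does the ±5-point margin per country need changing because the sample is a social-media convenience sample?

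*Combined protocol and SAP*

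**What the plan says.** In Technical design, item 7 (Sampling), the plan takes a prevalence of 28.4% from an earlier student survey and states "prevalence rate and a 5% error margin with a 95% confidence interval, the sample size required for each country is 312". It continues: "After adding a 10% nonresponse rate, the final sample size is about 343 for each country, so the total sample size will be 3773". Item 8 reads "Sampling Technique: Convenience Sampling". Operational design, item 3 (Data collection method), gives the route: "An online questionnaire will be shared via social media platforms, including Facebook, WhatsApp, and Telegram".

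The first objective is regional: "To assess the prevalence of GERD among medical students and interns in the Middle East". The Statistical analysis section summarises categorical variables as counts and percentages and names no confidence interval for prevalence. University is not among the items listed in the second questionnaire section ("associated risk factors such as age, sex, residency, GPA, smoking, BMI, and eating habits"), though that list is open-ended. The plan gives no design effect, sampling frame or number invited, and no statement of what the 5% leaves out.

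**The concern.** A margin of error with 95% confidence has its usual meaning only under probability sampling. Here an open link circulates on social media, and whoever chooses to answer does so. Students with reflux symptoms may be more willing, or less willing, to complete a long reflux questionnaire. Students from one university may also resemble each other. A reader who takes ±5 points at face value could think each country's prevalence better known than it is, and this is the only precision figure in the plan.

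Two further points follow. The plan does not say whether 343 counts people approached or questionnaires completed; under the first reading, its own 10% nonresponse leaves fewer than 312. And if answers are correlated within universities, the planned tests and regression could give p-values that are too small for predictors that differ mainly between universities.

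**Working it through.** **Inputs from the plan.** Prevalence p = 0.284, margin d = 0.05, 95% confidence (z = 1.96) and 10% nonresponse come from Sampling. The 11 countries come from Setting. GerdQ sensitivity 65% and specificity 71% come from Data collection method. The documents give no design effect, intracluster correlation or response ratio, so every such value below is an assumption.

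**1. The plan's figures.**
- n = z² p(1 − p)/d² = 3.8416 × 0.284 × 0.716 / 0.0025 = 312.47; stated 312.
- 312 × 1.10 = 343.2; stated 343.
- 343 × 11 = 3,773; stated 3,773.

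All three reproduce, with a design effect of 1.

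**2. What 343 counts.** Half-width = 1.96 × √(0.284 × 0.716 / n).
- 343 completed: ±4.77 points.
- 312 completed: ±5.00 points.
- 343 approached: 343 × 0.90 = 308.7, about 309 completed, ±5.03 points.

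Inflating by division would give 312/0.90 = 346.7, so 347, or 4 more people per country. The worse reading costs 0.03 of a point against the target.

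**3. Clustering (assumed design effects).** The half-width is multiplied by the square root of the design effect. With 343 completed:
- 1.5: 4.772 × 1.225 = ±5.8 points.
- 2.0: 4.772 × 1.414 = ±6.7 points.

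The ±5 holds up to 343/312.47 = 1.10. Restoring it at a design effect of 2 would need 2 × 312.47 = 624.9, so 625 per country and 625 × 11 = 6,875 in total. Nothing in the documents says whether 1.1, 1.5 or 2 is realistic, or that university is the right cluster.

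**4. Self-selection (assumed response ratios).** If students with GERD answer r times as readily, the expected observed prevalence is rp/(rp + 1 − p).
- r = 1.25: 0.355/(0.355 + 0.716) = 33.1%, a bias of +4.7 points.
- A bias of +5 points needs r = (0.334/0.666)/(0.284/0.716) = 1.26.
- A bias of −5 points needs r = (0.234/0.766)/(0.284/0.716) = 0.77.

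The sample size does not enter these expressions. At r = 1.25 with n = 312, the standard error is √(0.3315 × 0.6685/312) = 0.0267. The bias is then 0.0475/0.0267 = 1.78 standard errors, and a nominal 95% interval covers the truth about 57% of the time. With n = 625 the standard error is 0.0188, the ratio is 2.52, and coverage falls to about 29%. Recruiting more makes the nominal interval narrower around the same bias.

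**5. Misclassification (the plan's own accuracy figures).** If 28.4% were true disease prevalence, which is an assumption, the expected proportion at or above the GerdQ cut-off would be 0.65 × 0.284 + 0.29 × 0.716 = 0.185 + 0.208 = 39.2%. That is a shift of 10.8 points, larger than the 5-point selection bias above. It too is unaffected by sample size.

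**The case for a change.** The best case for a change is that it is cheap. One sentence could call the margin nominal and say what it excludes, another could define 343 as completed questionnaires, and a third could promise an interval for each prevalence. University could be recorded and cluster-robust standard errors used. Naming convenience sampling in a separate item is not the same as telling the reader what it does to the margin.

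Part of this stands. The margin is nominal, the plan does not say so, and the report should. But the first three additions are disclosure: they alter no estimate, test or recruitment target. The clustering proposal would change the analysis, yet it rests on an assumed cluster and an unknown correlation, may matter little for predictors that vary mainly within universities, and is unreliable in a country with few universities. It also does nothing about self-selection. It suits an optional sensitivity analysis if university turns out to be recorded.

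The Rationale may seem to offer evidence that such surveys are unstable, since one Egyptian survey is cited at 17.1% and another at 28.4%, 11.3 points apart. The same paragraph reports two Saudi surveys at 23.8% and 23.1%, 0.7 points apart. The documents give neither the sizes nor the recruitment methods of these four surveys, so neither pair settles anything.

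**Conclusion.** No change to the plan follows. The 312 is a simple-random-sample figure used as a planning input for a convenience sample whose nature is stated in the next item. It is a conventional way to set a recruitment target, and the plan makes no later claim that results will be accurate to ±5 points. The errors it leaves out are real, but none is repaired by a different number. Self-selection and misclassification do not shrink with sample size, and a clustering allowance cannot be set from these documents.

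The ambiguity over 343 is worth at most 0.26 of a point of nominal half-width (5.03 − 4.77). The wording about a final and a total sample size reads most naturally as completed questionnaires, which are also the quantity a team sharing an open link can count. On that reading the 312 is met with room to spare.

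Analysts can fill the remaining gap when reporting, by giving prevalence with a 95% interval and stating that it reflects random error only. The half-widths rest on the assumed 28.4%. The clustering and self-selection illustrations also rest on assumed design effects and response ratios, and the misclassification shift on reading 28.4% as true prevalence. The conclusion does not depend on their exact values.

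### The online form has no stated limit on repeat responses and no check for careless answering; random answering would raise reported GERD prevalence, and the safeguards must be built in before the link is shared

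*Combined protocol and SAP*

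**What the plan says.** Under Operational design, section 3 (Data collection method), recruitment is by social media: "An online questionnaire will be shared via social media platforms, including Facebook, WhatsApp, and Telegram". Technical design, item 8, gives "Sampling Technique: Convenience Sampling". The only exclusion criterion (Technical design, item 6) is "Students or interns who refused to participate".

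The four instruments, in the order respondents meet them, are:

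- GERDQ: "It is composed of 6 Likert scale questions that ask about GERD symptoms". On scoring, "Each question has 4 answers scored from 0 to 3, making a rank from 0 to 18", and on the cut-off, "If the participant scores 8 or more, this diagnoses GERD".
- GERD-HRQL: "This is a 16 Likert scale questionnaire that asks about the effect of GERD symptoms on the quality of life". Fifteen of the 16 items form the score.
- DEBQ: "This is a 33 Likert scale questionnaire that assesses the eating behavior", with items scored 1 to 5.
- DASS-21: 21 items scored 0 to 3, with each subscale sum doubled.

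The pilot (Operational design, section 1) uses Cronbach's alpha to assess the reliability of the questions. Section 4 (Statistical analysis) plans correlations among all four scores and a significance cut-off of 0.05. It contains no data-cleaning, duplicate, attention, completion-time or identical-answer rule.

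**The concern.** A long form circulated on social media will probably draw some inattentive respondents and some repeat submissions. Cronbach's alpha in a pilot does not identify either in the main data. Because no rule is stated, any removal decided after the data are seen would be ad hoc.

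Two things are at stake. The first is prevalence (objective 1): GERD is defined by a sum of 8 or more on a 0 to 18 scale, and random answers centre on 9, so they mostly fall on the GERD side. The second is the associations (objectives 2, 4 and 5): respondents who answer several scales carelessly share a common artefact across those scales, which can create or distort correlations. A larger sample narrows the interval around a shifted value without moving the value back.

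**Working it through.** **The plan's own figure.** Technical design, item 7, uses a prevalence of 28.4%, a margin of 5 points and 95% confidence: n = 1.96² × 0.284 × 0.716 / 0.05² ≈ 312.5, stated as 312. Then 312 × 1.10 = 343.2, stated as 343, and 343 × 11 = 3,773. All three reproduce.

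**Form length.** 6 + 16 + 33 + 21 = 76 instrument items (75 enter a score, since the sixteenth GERD-HRQL item does not), before the sociodemographic and risk-factor questions.

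**A random answerer on GERDQ.** Six items with four equally likely answers give 4⁶ = 4,096 patterns. The numbers of patterns summing to 0, 1, …, 7 are 1, 6, 21, 56, 120, 216, 336 and 456, in total 1,212. So P(score ≥ 8) = (4,096 − 1,212)/4,096 = 2,884/4,096 = 70.4%.

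**Effect on prevalence.** With a share c answering at random and true prevalence p, the reported value is (1 − c)p + 0.704c. The documents give no c; 2% to 10% is an assumed range. The values of p are the highest and lowest student prevalences cited in the Rationale.

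| c | p = 28.4% | p = 17.1% |
|---|---|---|
| 2% | 29.2% | 18.2% |
| 5% | 30.5% | 19.8% |
| 10% | 32.6% | 22.4% |

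The shift equals the 5-point country margin at c = 5/(70.4 − 28.4) = 11.9%, or 5/(70.4 − 17.1) = 9.4%. For the pooled sample, the nominal half-width at 28.4% is 1.96 × √(0.284 × 0.716/3,773) = 1.44 points, which is matched at c = 1.44/42.0 = 3.4%.

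**Other careless patterns.** One identical answer to all six GERDQ items scores 0, 6, 12 or 18.

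- Always the lowest answer: never GERD, so 28.4% becomes 0.95 × 28.4 = 27.0% at c = 5% and 25.6% at 10%.
- Column chosen evenly: half are GERD, so 28.4% becomes 29.5% at 5%.
- A mix of random answerers and lowest-answer respondents raises prevalence only if random answerers exceed 0.284/0.704 = 40% of the mix.

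**Correlations.** For two scores with genuine means m, SDs s and correlation r, and random-answer means n, the mixture covariance is (1 − c)·r·s₁s₂ + c(1 − c)(n₁ − m₁)(n₂ − m₂). Each variance is (1 − c)s² + c·t² + c(1 − c)(n − m)², where t is the random-answer SD. Random-answer means are 9 (GERDQ), 37.5 (GERD-HRQL), 21 (doubled DASS subscale) and 3.0 (DEBQ). The genuine means and SDs are assumptions; GERDQ is set at mean 5.5, SD 3.5, which gives about 28.4% at 8 or more under a normal approximation.

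| GERDQ with (assumed mean, SD) | true r | r at c = 5% | r at c = 10% |
|---|---|---|---|
| GERD-HRQL (10, 10) | 0 | 0.11 | 0.19 |
| GERD-HRQL (10, 10) | 0.70 | 0.68 | 0.67 |
| DASS subscale (10, 9) | 0 | 0.06 | 0.10 |
| DASS subscale (18, 11) | 0.50 | 0.49 | 0.48 |
| DEBQ, 10 items (3.0, 0.7) | 0.30 | 0.29 | 0.27 |
| DEBQ, 10 items (3.3, 0.6) | 0.30 | 0.26 | 0.22 |

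At n = 3,773, p < 0.05 needs only |r| ≈ 1.96/√3,773 = 0.032, so a null association between low-centred scores could be declared significant.

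**Repeat submissions.** If 10% of 312 records are repeats, about 281 distinct respondents remain and the half-width is 1.96 × √(0.284 × 0.716/281) = 5.3 points instead of 5.0.

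**The case against.** A reader might infer that careless answering must push prevalence and every correlation upwards. The documents do not support that. They give no mean or SD for any scale, and the Rationale's statement that medical students carry raised stress and anxiety argues against assuming low DASS-21 scores. Inflation needs genuine means below the random midpoint on both scales and a weak to moderate true correlation; otherwise correlations hold steady or fall. Prevalence also falls under lowest-answer responding. A reader might equally infer that every submission will be kept. The plan is silent on this; it does not say so.

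A further objection concerns order. GERDQ is the first instrument, so fatigue over a long form would mostly affect the DEBQ and DASS-21 blocks. If GERDQ is answered carefully and only DASS-21 at random (assumed mean 10, SD 9), prevalence does not move, a null correlation stays null, and 0.30 falls to 0.28 at c = 5% or 0.26 at 10%. This stands: the prevalence shift needs carelessness that is already present in the GERDQ section, and the length of the form alone does not establish that.

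Finally, a 2% to 10% random share leaves the country-level shift (+0.8 to +4.2 points) within the planned 5-point margin. That is correct, but the margin describes sampling error and does not allow for bias, and objective 1 is regional, where the nominal interval is much narrower.

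None of this supplies the missing rule. Where the direction is uncertain, a prespecified comparison with and without flagged records is the way to show how far the results depend on them.

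**Conclusion.** The gap is real and worth closing: no repeat-response limit and no check of individual submissions is described. Given uniform random answering that reaches GERDQ, the 70.4% figure is exact, and prevalence rises by about 2.1 points from 28.4% for each 5% of respondents answering that way. The careless share, its pattern and the genuine score distributions are not in the documents, so the size is a conditional range and the direction is not guaranteed. Correlations may be inflated (weak ones among GERDQ, GERD-HRQL and DASS-21) or diluted (DEBQ, and strong ones). Repeats have no fixed direction and mainly make precision look better than it is. The point goes beyond reporting detail because attention items and a one-response setting cannot be added once the data are in.

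**What to change.** Before the link is shared, in Operational design, section 3:

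- Set the form to one response per account.
- Add two instructed-response items with four options each, one directly after the GERDQ block and one within the DASS-21 block. Have them ask for different option positions, so that someone using a single column fails at least one.

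In section 4, prespecify that:

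- A record is flagged if it fails either item, or gives one identical answer to all 33 DEBQ items.
- The number flagged is reported.
- Prevalence and the main associations are reported with and without flagged records, the analysis without them being primary.

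The either-item rule matters. A random answerer passes both four-option items with probability 1/4 × 1/4 = 1/16, so about 94% are flagged; requiring failure of both would flag only 0.75² = 56%. At c = 5%, the random share left is 0.003125/(0.95 + 0.003125) = 0.33%, and the shift from 28.4% falls from 2.1 to about 0.14 points, if careful respondents all pass.

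The cost is two short items, one form setting and a few sentences in section 4. Some records will be lost from the primary analysis, including some with valid GERDQ answers from respondents who tired later, or from people who genuinely give one answer throughout DEBQ. A sign-in step may deter a few students, and it does not stop someone who holds several accounts.
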